12. Persons deprived of liberty could be eligible because the expected benefice (improvement of disease control rate) justifies the foreseeable risk (adverse reaction of nivolumab).

4.2 Exclusion Criteria:

1. Concurrent malignancies requiring active intervention
2. Active Infection
3. Patient with known EGFR activating tumor mutation or known ALK or ROS1 gene rearrangement not treated with the appropriate targeted therapy.
4. History of immunological events related to HIV: lymphoid interstitial pneumonitis (LIP), non-infectious uveitis, encephalitis and other manifestations of CD8 lymphocyte infiltration syndrome, HIV-associated nephropathy (HIVAN).
5. Subjects with active, known or suspected autoimmune disease. Subjects with vitiligo, type I diabetes mellitus, residual hypothyroidism due to autoimmune thyroiditis only requiring hormone replacement, or conditions not expected to recur in the absence of an external trigger are permitted to enroll.
6. Active or history of inflammatory bowel disease (eg, diverticulitis, colitis, Crohn's, coeliac disease or other serious gastrointestinal chronic conditions associated with diarrhea). Note that diverticulosis is permitted.

7. Symptomatic cerebral metastasis unless treated by brain radiotherapy which will be completed for at least 15 days before the beginning of the treatment; subjects with carcinomatous meningitis.
8. Prior treatment with an anti-PD-1, anti-PD-L1, anti-PD-L2, anti-CTLA-4 antibody, or any other antibody or drug specifically targeting T-cell co-stimulation or checkpoint pathways.
9. The last dose of prior chemotherapy or radiation therapy (with the exception of palliative radiotherapy) was received less than 3 weeks prior to inclusion;
10. History of primary immunodeficiency, history of organ transplant that requires therapeutic immunosuppression and the use of immunosuppressive agents within 28 days of inclusion or a prior history of severe (grade 3 or 4) immune mediated toxicity from other immune therapy.
11. Subjects with a condition requiring systemic treatment with either corticosteroids (> 10 mg daily prednisone equivalent) or other immunosuppressive medications within 14 days of inclusion. Intranasal/inhaled or topical steroids, and adrenal replacement steroid doses \leq 10 mg daily prednisone equivalent, are permitted in the absence of active autoimmune disease.

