5.1 Authorized concomitant treatment

Subjects are permitted the use of topical, ocular, intra-articular, intranasal, corticosteroids (with minimal systemic absorption). Adrenal replacement steroids dosed $<$ 10 mg daily prednisone are permitted. A brief (less than 3 weeks) course of corticosteroids \geq for prophylaxis (eg, contrast dye allergy) or for treatment of non-autoimmune conditions is permitted.

Concomitant palliative and supportive care for disease related symptoms is allowed if initiated prior to first dose of study therapy. Prior palliative radiotherapy must have been completed at least 2 weeks prior to inclusion.

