6.2 Early treatment termination

The investigator may terminate a patient's participation early in the event of:

- Tumour progression during treatment
- Toxicity requiring termination of study treatments
- Intercurrent illness
- Protocol violation
- Non-compliance (nivolumab)
- Administrative reasons
- Pregnancy

7 PRE-TREATMENT EVALUATION:

Investigations		Timing
History and Physical Exam including:	
 history including (occupational), smoking history physical examination including height, weight, pulse, blood pressure performance status (PS) 	Within 14 days of inclusion
Haematology	
 CBC including haemoglobin, differential, platelet count 	Within 14 days of inclusion
Biochemistry	
 AST (SGOT) and ALT (SGPT) alkaline phosphatase bilirubin albumin serum creatinine lipase fasting glucose K, Cl, Na, Mg, Ca, P LDH CRP TSH (T3, T4 if TSH abnormal) INR/APTT 	Within 14 days of inclusion
Immunovirology	
 Serology EBV, HCV/HBV, CMV, Toxoplasmosis - TPHA-VDRL, HHV-8 Quantiferon 	Before inclusion
	
 CD4/CD8 cell counts HIV viral load (VL) HCV/HBV VL, HHV-8 VL in the case of co-infection EBV VL, CMV VL 	Within 28 days of inclusion ; those VL will be monitored further in case of positivity
Radiology ¹	
 baseline CT brain, chest and abdomen (with iodine injection) (Wang 2004) baseline PET-CT : highly recommended (but optional) (Ceresoli 2006b, von Schulthess 2006, Francis 2007) 	Within 28 days of inclusion
	
 other baseline imaging (e.g. bone scan,...) 	Required, within 28 days of inclusion, only if suspicious signs/symptoms are present
Correlatives	
 tumour tissue for assessment of PD-L1 status 	From initial diagnosis block

	
 whole blood, serum, plasma for correlatives 	Prior to cycle 1, day 1 dosing
Other Investigations	
 ECG 	Within 14 days of inclusion
	
 pregnancy test if applicable 	Within 24hrs of first drug administration
Adverse Event	Baseline adverse event evaluation (to document residual adverse event from previous therapy and baseline symptoms)	Within 14 days of inclusion
Quality of Life	LCSS questionnaire	Within 14 days of inclusion

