9 STUDY TREATMENT

The study treatments are explained in table 1.

Table 1.

Active substance	Nivolumab
Commercial Name	Opdivo [®]
Pharmaceutical form	Concentrate for solution for infusion
Dosage	10 mg/mL
Posology	3mg/kg
Storage	Store in refrigerator (2°C - 8°C) in its original package in order to protect from light
Laboratory	BMS

The treatment has to begin within 15 days following inclusion.

These treatments will be labeled according to the regulation. These treatments will be administered until progression or limiting toxicities.

Nivolumab has a concentration of 10mg/mL and is provided in a 10mL vial.

Storage Conditions & Handling:

- Store at 2-8°C (36-46°F), protect from light, freezing, and shaking.
- If any temperature excursions are encountered during storage, please report these to IFCT for assessment via the Temperature Excursion Response Form.
- As with all injectable drugs, care should be taken when handling and preparing nivolumab. Whenever possible, nivolumab should be prepared in a laminar flow hood or safety cabinet using standard precautions for the safe handling of intravenous agents applying aseptic technique.

- Partially used vials should be disposed at the site following procedures for the disposal of anticancer drugs.

Use Time/Stability: Please refer to the appropriate section of the current Investigator Brochure or Addendum. Due to parameters surrounding the use time of nivolumab, the time of preparation should be noted in the Pharmacy Source documents [accountability logs] or in study files as required for investigator sponsored research [FDA and GCP]

The administration of nivolumab infusion must be completed within 24 hours of preparation. If not used immediately, the infusion solution may be stored up to 20 hours in a refrigerator at under refrigeration conditions (2° - 8°C, 36° - 46°F) and used within 24 hours, and a maximum of 4 hours of the total 24 hours can be at room temperature (20° - 25°C, 68° - 77°F) and under room light. The maximum 4-hour period under room temperature and room light conditions for undiluted and diluted solutions of nivolumab injection in the IV bag includes the product administration period.

Preparation and Administration:

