13.4 Efficacy Analyses

13.4.1 Primary endpoint analysis

Analysis of the primary efficacy endpoint will be conducted on all eligible patients, based on the disease control rate after 8 weeks of treatment. Analysis of the primary efficacy endpoint will be also conducted on all patients (ITT analysis) as sensitivity analysis.

It will be presented associated with its 95% confidence interval. Patients for whom the answer cannot be evaluated will be considered as treatment failures.

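### The baseline CT is timed to inclusion, so it may be up to 43 days old at the first dose and may precede the end of prior anticancer treatment

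*Protocol*

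**What the plan says.** Protocol section 7 (pre-treatment evaluation, radiology rows) asks for "baseline CT brain, chest and abdomen (with iodine injection") with the timing "Within 28 days of inclusion". Section 9 adds: "The treatment has to begin within 15 days following inclusion".

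The anticancer washouts are set elsewhere:

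- Section 4.2, criterion 9, excludes a patient if "The last dose of prior chemotherapy or radiation therapy (with the exception of palliative radiotherapy) was received less than 3 weeks prior to inclusion".
- Section 5.1 covers the palliative radiotherapy that criterion 9 exempts: "Prior palliative radiotherapy must have been completed at least 2 weeks prior to inclusion".
- Section 4.2, criterion 7, has a separate rule for symptomatic brain metastases, counted to treatment and not to inclusion: "brain radiotherapy which will be completed for at least 15 days before the beginning of the treatment".

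The primary analysis in section 13.4.1 is "based on the disease control rate after 8 weeks of treatment". Section 13.2 tests that rate against 30% in a single arm. Section 8.1 runs the on-study CT every 8 weeks counted from randomisation, although the trial is not randomised, and keeps that schedule whatever the treatment delays.

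In the text at hand, no rule limits the time from baseline CT to first dose, and none requires the scan to follow the end of prior treatment.

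**The concern.** Disease control at the first evaluation compares the 8-week scan with the baseline scan. Whatever happens to the tumour between baseline and first dose enters that comparison, and there is no control arm in which the same thing happens.

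Two routes of bias follow, in opposite directions. Patients enter with recurrence or progression during or after platinum, so growth between the scan and the first dose is plausible; it counts against nivolumab and lowers the rate. Anticancer treatment given after the baseline scan can shrink a measured lesion, which counts in favour of nivolumab and raises the rate. Both depend on how sites schedule the scan, not on the drug. An analysis plan cannot repair a baseline taken at the wrong time, so the protocol has to fix the timing.

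**Working it through.** **Inputs from the protocol.** CT window: 28 days before inclusion (section 7). Inclusion to first dose: at most 15 days (section 9). Washouts to inclusion: 21 days for chemotherapy and non-palliative radiotherapy (section 4.2), 14 days for palliative radiotherapy (section 5.1). First evaluation: 8 weeks = 56 days (section 13.2). Decision rule: stop for futility at 4 or fewer controlled of 14; positive at 13 or more of 28; 30% against 57%.

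**Age of the baseline at first dose.** 28 + 15 = 43 days at most.

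**Scan against end of prior treatment, all counted to inclusion.**
- Last chemotherapy dose: 28 − 21 = 7 days after the scan at most.
- End of palliative radiotherapy: 28 − 14 = 14 days after the scan at most.

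**What the deciding comparison spans at these maxima.**
- 8-week scan counted from inclusion: 28 + 56 = 84 days between scans, of which 56 − 15 = 41 follow the first dose (41/84 = 49%).
- 8-week scan counted from first dose: 43 + 56 = 99 days between scans, of which 56 follow the first dose (56/99 = 57%).

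**The plan's own rule.** Exact binomial calculation for 13 of 28, ignoring the interim look: type I error 0.049, power 0.906. With the futility stop: 0.047 and 0.896. The stated 5% and 90% (reading the printed β as power) are reproduced, so the design figures are not in question.

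**Illustration of growth (assumed; the protocol gives no growth rate).** With exponential growth and volume doubling time DT, diameter grows by the factor 2^(t/(3·DT)).

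| DT (days) | t = 43 | t = 28 | Difference, percentage points |
|---|---|---|---|
| 60 | 1.180 | 1.114 | 6.6 |
| 100 | 1.104 | 1.067 | 3.8 |
| 150 | 1.068 | 1.044 | 2.4 |

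The last column is the most that moving the 28-day window to the first dose could remove under these assumptions.

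**Illustration of the effect on the decision (assumed shares, two-stage rule).**
- If 5% or 10% of truly controlled patients are scored as progressing, the rate under the alternative falls from 0.57 to 0.57 × 0.95 = 0.5415 or 0.57 × 0.90 = 0.513. Power falls from 0.896 to 0.83 or 0.74.
- If 5% or 10% of true progressors are scored as controlled, the rate under the null rises from 0.30 to 0.30 + 0.70 × 0.05 = 0.335 or 0.30 + 0.70 × 0.10 = 0.37. Type I error rises from 0.047 to 0.10 or 0.19.

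These lines show sensitivity only. Nothing in the protocol says what share of patients would be affected.

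**The case against.** The strongest reply is that this is a scheduling preference. Most screening windows in section 7 are counted to inclusion, and PFS and OS start there, so the anchor is consistent. Growth before dosing works against nivolumab, which is conservative for a positive claim. The two biases oppose each other and no net direction is shown. All of this stands, and it limits the weight of the point. It does not remove it: a conservative bias still costs power in a 30-patient trial in a rare population, and the same section 7 table already ties other items, such as the pregnancy test and the correlative samples, to dosing.

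Several stronger readings are tempting but unsupported:

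- *The CT window is longer than every washout.* It is not. Section 4.2, criterion 10, bars "the use of immunosuppressive agents within 28 days of inclusion", which equals the CT window. The statement holds for the anticancer washouts counted to inclusion.
- *Palliative radiotherapy may end up to 28 days after the scan because criterion 9 exempts it.* Section 5.1 closes that gap at 14 days.
- *Brain radiotherapy may end 28 days after the scan (43 − 15).* This follows only if criterion 7 is read alone. If section 5.1 or criterion 9 also applies, the limit is 14 or 7 days.
- *Chemotherapy after the scan would inflate the rate.* The route is thin: at most 7 days, in patients who have already progressed or recurred. Radiotherapy is the more credible upward route, and only when it reaches a measured lesion.
- *Growth alone would turn controlled patients into progressors.* Even the fastest assumed case reaches 18% in 43 days, and most of the assumed growth remains with a 28-day limit.

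Finally, the radiology row carries a footnote mark whose text is not shown, and the design figure is missing. Either might address baseline timing.

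**Conclusion.** The point holds as a cheap improvement, not as a flaw that invalidates the design. By the stated windows, a compliant baseline CT can be up to 43 days old at first dose and can precede the last chemotherapy dose by up to 7 days or the end of palliative radiotherapy by up to 14. These are permitted maxima; the protocol does not give the usual gap. The conclusion assumes that the unseen radiology footnote does not already limit the timing.

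The likelier bias is downward, from growth before dosing. An upward bias from radiotherapy to measured lesions is possible. Neither the size nor the net direction can be derived from the protocol, and the growth and reclassification figures above are illustrations.

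A related and firmer inconsistency is the origin of the deciding scan. Section 8.1 counts from a randomisation that does not exist, while section 13.4.1 speaks of 8 weeks of treatment. If the count runs from inclusion, as few as 41 days may have passed since the first dose.

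**What to change.** In the radiology rows of section 7, require the baseline CT to be done after the end of prior anticancer treatment, including palliative radiotherapy to a measurable lesion, and within 28 days before the first nivolumab infusion. The 15-day limit in section 9 can stay; sites would mostly comply by timing the first infusion to a scan already done. If the radiology footnote already says something on timing, align it.

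Reconcile sections 8.1 and 13.4.1 so that both name the same existing origin for the 8-week scan, and so that the endpoint wording matches it.

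The sample size, decision rule and analysis do not change. The cost is tighter scheduling across the twenty planned centres and an occasional repeat contrast CT, when a scan ages out or precedes the last prior treatment. The change cuts the maximum baseline age from 43 to 28 days; it does not remove growth within those 28 days.

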8 EVALUATION DURING AND AFTER PROTOCOL TREATMENT

8.1 Evaluation during Protocol Treatment

	Investigations	Timing
History and Physical Exam including:	
 physical examination including, pulse, blood pressure, weight performance status 	Prior to each infusion until off protocol therapy
Hematology	
 CBC including hemoglobin, differential, platelet count 	Prior to each infusion until off protocol therapy
Biochemistry	
 AST (SGOT) and ALT (SGPT) alkaline phosphatase, gamma GT Bilirubin, LDH albumin creatinine, urea lipase (and amylase if abnormal lipase) fasting glucose K, Cl, Na, Ca, Mg²⁺ Urinary test 	Prior to each infusion until off protocol therapy
	
 TSH (T3, T4 if TSH abnormal) Antinuclear antibody and in case of positivity anti-ENA and anti-DNA; anti-thyroperoxydase, anti-thyroglobulin 	Every 6 weeks, until off protocol therapy
Immunolovirology (2)	
 Hbs antigen, HCV/HBV VL, HHV-8 VL in the case of co-infection EBV VL, CMV VL, 	Cycle 2, 3, 9, 15, 27, 51, end of treatment and in case of immune related adverse event. Every 3 cycles for Hbs antigen, HCV/HBV VL

Immunolovirology (1)	
 CD4/CD8 cell counts HIV viral load (VL) 	Prior to each infusion until off protocol therapy
Radiology*	
 CT-scan of chest and upper abdomen Other imaging used for baseline tumoral assessment 	Every 8 weeks from randomization (CTs schedule must be maintained regardless of treatment delays)
Other Investigations	
 ECG 	As clinically indicated
	
 lung function tests: FEV1, FVC, TLCO and blood gas at room atmosphere 	Only if pulmonary symptoms or suspicion of pneumonitis
	
 pregnancy test if applicable 	Every 3 cycles ± 1 weeks
Correlatives	
 whole blood, serum, plasma 	Cycle 2, 3, 9, 15, 27, 51, end of treatment and in case of immune related adverse event.
Adverse Events	patients must be evaluated at each visit for adverse events according to CTCAE v4	
Quality of Life	
 LCSS questionnaire 	Cycle 2, 3, 5, 7, 9

* Radiology assessments must be kept to schedule irrespective of any delays in a treatment cycle. If the schedule cannot be kept all attempts must be made to undertake the required imaging as soon as possible. Thereafter, patients must be put back on original imaging schedule.

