2.2 Secondary objectives/endpoints

- tolerance: Adverse Events (AEs) grade (NCI-CTC 4.0),
- impact on HIV control and immunological (CD4, CD8, HIV viral load each evaluation), other associated chronic infection susceptible of reactivation (HHV8, CMV, EBV, tuberculosis) and potential occurrence of autoimmunity (organ specific i.e. thyroiditis, adrenalitis and hypophysitis, or non organ specific)
- duration of response
- Responses rate according to tissue PD-L1 expression
- progression-free survival
- Overall survival
- Quality of life (LCSS)

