3 REGIMEN

Thirty eligible patients, previously treated by at least one line of platinum-based chemotherapy, will be included.

[figure not shown]
TREATMENT:

Nivolumab is administered intravenously (IV), over 30 minutes at 3 mg/kg every 2 weeks, until disease progression, death, limiting toxicity or patient refusal.

Premedication is not required.

Patients with tumoral progression will stop the treatment but will have a follow-up for the secondary endpoints of OS, and the toxicities assessment till a last study visit 4 weeks (\pm 1 week) after the last injection of the drug.

Twenty centers will be opened.

Schedule of the study design.

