8.2 Evaluation after protocol treatment

	Investigations	Timing
History and Physical Exam including:	
 physical examination including, pulse, blood pressure, weight performance status 	Within 30 days following last treatment day
Hematology	
 CBC including haemoglobin, differential, platelet count 	Within 30 days following last treatment day
Biochemistry	
 AST (SGOT) and ALT (SGPT) alkaline phosphatase bilirubin albumin creatinine lipase (and amylase if abnormal lipase) fasting glucose K, Cl, Na, Ca 	Within 30 days following last treatment day
	
 TSH (T3, T4 if TSH abnormal) 	As clinically indicated
Radiology*	
 CT-scan of chest and upper abdomen 	Every 8 weeks
Other	
 ECG 	As clinically indicated

Investigations	
• lung function tests: FEV1, FVC, TLCO and blood gas at room atmosphere	As clinically indicated
Adverse Events	Patients must be evaluated for treatment related adverse events until resolution	

* Only for patients who have not yet discontinued the study treatment

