13.2 Sample size assumption

It is a phase II non randomized, multicenter, open study, assessing nivolumab efficacy.

Tested hypothesis

The hypothesis underscoring our study is that the disease is controlled (stable disease or response) in at least 57% of patients at first evaluation (8 weeks) of nivolumab therapy.

H_0 : control rate $\leq 30\%$ (unacceptable control rate)

H_1 : control rate $\geq 57\%$ (acceptable control rate)

$\alpha=5\%$ (one-sided), $\beta=90\%$

Step 1 (n=14 patients): ≤ 4 patients with a disease controlled \rightarrow futility (H_0 accepted)

Final decision (n=28 patients): ≥ 13 patients with a disease controlled \rightarrow rejected H_0 (positive trial)

30 patients included, taking into account possible non eligible patients (5%)

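### After baseline, LCSS is collected only at cycles 2, 3, 5, 7 and 9, so patients who stop nivolumab give no quality-of-life data after stopping, and later means are likely to be too favourable

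*Protocol*

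**What the plan says.** Protocol section 2.2 lists quality of life, measured by LCSS, among the secondary endpoints. Three places bear on when it is collected.

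- **Before treatment.** The table in section 7 schedules a baseline form: "Quality of Life LCSS questionnaire Within 14 days of inclusion".
- **During treatment.** The table in section 8.1 gives "LCSS questionnaire Cycle 2, 3, 5, 7, 9". In the same table, the correlative samples and the second immunovirology row are scheduled at "Cycle 2, 3, 9, 15, 27, 51, end of treatment and in case of immune related adverse event". The LCSS row has no end-of-treatment entry.
- **After treatment.** The table in section 8.2 schedules physical examination, performance status and laboratory tests "Within 30 days following last treatment day". It has no quality-of-life row.

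Section 3 sets dosing "every 2 weeks, until disease progression, death, limiting toxicity or patient refusal". It describes what follows progression as: "Patients with tumoral progression will stop the treatment but will have a follow-up for the secondary endpoints of OS, and the toxicities assessment". Quality of life is not named there.

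**The concern.** The LCSS schedule follows treatment cycles, and patients leave treatment mainly because of progression or toxicity. A patient who stops has no further scheduled form, so the patients whose quality of life is most likely to have fallen are the ones who drop out of the data.

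The first CT, at 8 weeks, is the first planned point at which many patients may stop, and cycle 5 falls at about the same time. Means from then on rest mainly on patients who continue. With a single arm, there is no comparator in which a similar loss could offset the distortion.

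This is a stated collection schedule and not a detail left open for a statistical analysis plan. An analysis plan can choose how to handle missing forms, but it cannot supply forms that the protocol does not request.

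**Working it through.** **Timing.** With 14-day cycles and no delays, cycle c is due at week 2 × (c − 1). Cycles 2, 3, 5, 7 and 9 fall at weeks 2, 4, 8, 12 and 16. A patient who stops after the week 8 CT and before cycle 5 has a last scheduled form at cycle 3, week 4. Patients still on treatment have no form after week 16.

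**The plan's own figures.** The protocol gives no figure for LCSS. The only usable inputs are the week 8 control rates in section 13.2: 30% under H0, and under H1 "the disease is controlled (stable disease or response) in at least 57% of patients at first evaluation (8 weeks) of nivolumab therapy". These belong to a design that reproduces. With 28 patients and a threshold of 13, exact one-sided alpha is 0.049 and power 0.906. With the futility stop at 4 or fewer of 14, they are 0.047 and 0.896. Also 28 / 0.95 = 29.5, rounded up to 30.

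**Patients without control at week 8.**
- H1: 1 − 0.57 = 0.43, and 0.43 × 28 = 12.0 patients (12.9 of 30).
- H0: 1 − 0.30 = 0.70, and 0.70 × 28 = 19.6 patients (21 of 30).

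**Bias in the on-treatment mean.** Let p be the control rate. Let uncontrolled patients score worse than controlled patients by d, in SD units. The value of d is an assumption, shown over a range. The all-patient mean then lies (1 − p)d on the worse side of the controlled mean.

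1. *All uncontrolled patients stop.* Only controlled patients are observed, so the bias is (1 − p)d: 0.43d under H1 and 0.70d under H0.
2. *Half continue beyond progression (assumption) with the same deficit d.* The bias is d × [uncontrolled share overall − uncontrolled share among those observed].
   - H1: 0.43 − 0.215 / (0.57 + 0.215) = 0.43 − 0.274 = 0.156, so 0.156d.
   - H0: 0.70 − 0.35 / (0.30 + 0.35) = 0.70 − 0.538 = 0.162, so 0.162d.
3. *Half continue and score like controlled patients.* The observed mean is the controlled mean, so the bias is 0.215d under H1 and 0.35d under H0.

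| Bias (SD), H1 / H0 | d = 0.25 | d = 0.5 | d = 0.8 |
|---|---|---|---|
| 1. All stop | 0.11 / 0.18 | 0.22 / 0.35 | 0.34 / 0.56 |
| 2. Half continue, same deficit | 0.04 / 0.04 | 0.08 / 0.08 | 0.12 / 0.13 |
| 3. Half continue, no deficit | 0.05 / 0.09 | 0.11 / 0.18 | 0.17 / 0.28 |

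**Against sampling error, H1, d = 0.5.** In case 1 about 0.57 × 28 = 16 patients are observed. The standard error is about 1/√16 = 0.25 SD, and the bias is 0.215 / 0.25 = 0.86 standard errors. In case 2 about 0.785 × 28 = 22 are observed. The standard error is about 1/√22 = 0.21 SD, and the bias is 0.078 / 0.213 = 0.37 standard errors.

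**The case against.** Several points on the other side stand and limit what can be claimed.

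- **Baseline exists.** A reader of the 8.1 table alone might infer that LCSS is collected only on treatment. Section 7 schedules a baseline form, so the gap is at and after stopping.
- **The direction is not documented.** A reader might infer that the result must be too favourable. That requires patients who stop to score worse. It is plausible, but the protocol gives no LCSS data, and the bias is zero if they score the same.
- **Not controlled is not the same as stopped.** Section 10 lets selected patients continue after first progression at the 8-week scan. The 0.43d to 0.70d figures are therefore an upper bound and not an estimate. Section 10 also requires clinical benefit, good tolerance and stable performance status, so the progressors who stop are likely to be those doing worse. Continuation reduces the bias without removing it.
- **Cycle 5 is not always missed.** CTs run every 8 weeks from what section 8.1 calls randomization, presumably inclusion in this single-arm trial. Section 10 allows ±1 week, and section 9 allows treatment to start up to 15 days after inclusion. Cycle 5 is then due about 56 to 71 days after inclusion, before the CT in some patients and after it in others. It does not follow that every progressor lacks a cycle 5 form.
- **Some data cannot exist.** Uncontrolled patients include those who died and those who could not be evaluated, who count as failures under section 13.4.1. Patients who died give no form under any schedule.
- **Deterioration is not wholly unrecorded.** Performance status is taken within 30 days of the last treatment, and adverse events are collected to 100 days. Only the patient's own LCSS score is missing.
- **The endpoint is modest.** LCSS is one of seven secondary items, without a decision rule. A schedule ending at cycle 9 is consistent with a short on-treatment description.

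None of this supplies a form after stopping.

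**Conclusion.** The concern holds in a limited form. After baseline, the protocol fixes LCSS at five treatment cycles and requests nothing at or after the end of treatment, although a suitable visit exists and neighbouring rows of the same table include that time point. LCSS results from about week 8 on will mainly represent patients still treated.

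At an assumed deficit of 0.5 SD, the on-treatment mean would be too favourable by roughly 0.08 SD (half of the uncontrolled patients continue with the same deficit) to 0.35 SD (all stop, H0). The size rests on three assumptions that the documents do not settle: the deficit d, its direction, and the share continuing beyond progression. Controlled patients who stop for toxicity are left out of the calculation, since the protocol gives no rate for them.

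This is an inexpensive improvement to a secondary endpoint. A reader might infer that it threatens the trial's main conclusion. It does not, because the disease control rate and the sample size do not depend on LCSS.

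**What to change.** - **Section 8.1:** add an end-of-treatment time point to the LCSS row, after cycles 2, 3, 5, 7 and 9.
- **Section 8.2:** add an LCSS row at the existing visit within 30 days of the last treatment, for every patient whatever the reason for stopping.
- **Reporting:** show the end-of-treatment form alongside the cycle-based results, and label means from cycle 5 on as on-treatment results.

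The added form captures deterioration around the time of stopping. It is not a week 8 measurement and does not remove the selection from the cycle 5 mean, which is why the labelling is also needed.

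The cost is one more short questionnaire per patient at a visit already planned, a small protocol amendment and a few lines of reporting. Some forms will still be missing for patients who die or are too ill. No change to the sample size is needed.
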